### 10.7.2 Response Criteria for Target Lesions

Response criteria are assessed based on the product of the longest diameter and its longest perpendicular diameter. Development of new disease or progression in any established lesions is considered progressive disease, regardless of response in other lesions – e.g., when multiple lesions show opposite responses, the progressive disease takes precedence. Response Criteria for target lesions:

- **Complete Response (CR):** Disappearance of all target and non-target lesions.
- **Partial response (PR):**  $\geq 50\%$  decrease in the sum of the products of the two perpendicular diameters of all target lesions (up to 5), taking as reference the initial baseline measurements.

- **Stable Disease (SD):** Neither sufficient decrease in the sum of the products of the two perpendicular diameters of all target lesions to qualify for PR, nor sufficient increase in a single target lesion to qualify for PD.
- **Progressive Disease (PD):** 25% or more increase in the product of perpendicular diameters of ANY target lesion, taking as reference the smallest product observed since the start of treatment, or the appearance of one or more new lesions.

10.7.3 Response Criteria for Non-Target Lesions:

- **Complete Response (CR):** Disappearance of all non-target lesions.
- **Incomplete Response/Stable Disease (IR/SD):** The persistence of one or more non-target lesions.
- **Progressive Disease (PD):** The appearance of one or more new lesions and/or unequivocal progression of existing non-target lesions.

10.7.4 Response criteria for tumor markers (if available):

Tumor markers will be classified simply as being at normal levels or at abnormally high levels.

10.7.5 Overall Response Assessment

The overall response assessment takes into account response in both target and non-target lesions, the appearance of new lesions and normalization of markers (where applicable), according to the criteria described in the table below. The overall response assessment is shown in the last column, and depends on the assessments of target, non-target, marker and new lesions in the preceding columns.

Target Lesions	Non-target Lesions	Markers	New Lesions	Overall Response
CR	CR	Normal	No	CR
CR	IR/SD	Normal	No	PR
CR	CR, IR/SD	Abnormal	No	PR
PR	CR, IR/SD	Any	No	PR
SD	CR, IR/SD	Any	No	SD
PD	Any	Any	Yes or No	PD
Any	PD	Any	Yes or No	PD
Any	Any	Any	Yes	PD

Each patient will be classified according to his “best response” for the purposes of analysis of treatment effect. Best response is determined as outlined in [Section 10.6](#) from a sequence of overall response assessments.

## 11.0 ADVERSE EVENT REPORTING REQUIREMENTS

### 11.1 Purpose

Adverse event (AE) data collection and reporting, which are required as part of every clinical trial, are done to ensure the safety of patients enrolled in the studies as well as those who will

enroll in future studies using similar agents. Certain adverse events must be reported in an expedited manner to allow for timelier monitoring of patient safety and care. The following sections provide information about expedited reporting.

## 11.2 Expedited Reporting Requirements – Serious Adverse Events (SAEs)

To ensure compliance with these regulations/this guidance, as IND/IDE sponsor, NCI requires that AEs be submitted according to the timeframes in the AE reporting table assigned to the protocol, using the CTEP Adverse Event Reporting System (CTEP-AERS).

***Any AE that is serious qualifies for expedited reporting.*** An AE is defined as any untoward medical occurrence associated with the use of a drug in humans, whether or not considered drug related. A Serious Adverse Event (SAE) is any adverse drug event (experience) occurring at any dose that results in ANY of the following outcomes:

- 1) Death.
- 2) A life-threatening adverse drug experience.
- 3) An adverse event resulting in inpatient hospitalization or prolongation of existing hospitalization (for  $\geq 24$  hours). This does not include hospitalizations that are part of routine medical practice.
- 4) A persistent or significant incapacity or substantial disruption of the ability to conduct normal life functions.
- 5) A congenital anomaly/birth defect.
- 6) Important Medical Events (IME) that may not result in death, be life threatening, or require hospitalization may be considered a serious adverse drug experience when, based upon medical judgment, they may jeopardize the patient or subject and may require medical or surgical intervention to prevent one of the outcomes listed in this definition.

## 11.3 Specific Examples for Expedited Reporting

### 11.3.1 SAEs Occurring More than 30 Days After Last Dose of Study Drug

Any Serious Adverse Event that occurs more than 30 days after the last administration of the investigational agent/intervention **and** has an attribution of a possible, probable, or definite relationship to the study therapy must be reported according to the CTEP-AERS reporting table in this protocol.

### 11.3.2 Persistent or Significant Disabilities/Incapacities

Any AE that results in persistent or significant incapacity or substantial disruption of the ability to conduct normal life functions (formerly referred to as disabilities), congenital anomalies or birth defects, must be reported via CTEP-AERS if it occurs at any time following treatment with an agent under a NCI IND/IDE since these are considered serious AEs.

### 11.3.3 Death

#### **Reportable Categories of Death**

- Death attributable to a CTCAE term.
- Death Neonatal: ***“Newborn deaths occurring during the first 28 days after birth”***
- Sudden Death NOS: A sudden (defined as instant or within one hour of the

onset of symptoms) or an unobserved cessation of life that cannot be attributed to a CTCAE term associated with Grade 5.

- Death NOS: A cessation of life that cannot be attributed to a CTCAE term associated with Grade 5.
- Death due to progressive disease should be reported as **Grade 5 “Disease progression”** under the system organ class (SOC) of “General disorder and administration site conditions”. Evidence that the death was a manifestation of underlying disease (e.g., radiological changes suggesting tumor growth or progression: clinical deterioration associated with a disease process) should be submitted.

Any death occurring **within 30 days** of the last dose, regardless of attribution to the investigational agent/intervention requires expedited reporting within 24 hours.

Any death occurring **greater than 30 days** after the last dose of the investigational agent/intervention requires expedited reporting within 24 hours **only if** it is possibly, probably, or definitely related to the investigational agent/intervention.

#### 11.3.4 Secondary Malignancy

A **secondary malignancy** is a cancer caused by treatment for a previous malignancy (e.g., treatment with investigational agent/intervention, radiation or chemotherapy). A metastasis of the initial neoplasm is not considered a secondary malignancy.

The NCI requires all secondary malignancies that occur following treatment with an agent under an NCI IND/IDE be reported via CTEP-AERS. Three options are available to describe the event:

- Leukemia secondary to oncology chemotherapy
- Myelodysplastic syndrome
- Treatment related secondary malignancy

Any malignancy possibly related to cancer treatment (including AML/MDS) must also be reported via the routine reporting mechanisms outlined in this protocol.

#### 11.3.5 Second Malignancy

A **second malignancy** is one unrelated to the treatment of a prior malignancy (and is **NOT** a metastasis from the initial malignancy). Second malignancies require **ONLY** routine reporting via CDUS unless otherwise specified.

#### 11.3.6 Pregnancy, Fetal Death, and Death Neonatal

NOTE: When submitting CTEP-AERS reports for “Pregnancy”, “Pregnancy loss”, or “Neonatal loss”, the Pregnancy Information Form, available at:

[http://ctep.cancer.gov/protocolDevelopment/electronic\\_applications/docs/Pregnancy\\_ReportForm.pdf](http://ctep.cancer.gov/protocolDevelopment/electronic_applications/docs/Pregnancy_ReportForm.pdf), needs to be completed and faxed along with any additional medical information to [contact]. The potential risk of exposure of the fetus to the investigational agent(s) or chemotherapy agent(s) should be documented in the “Description of Event” section of the CTEP-AERS report.

##### 11.3.6.1 **Pregnancy**

Patients who become pregnant on study risk intrauterine exposure of the fetus to agents that may be teratogenic. For this reason, pregnancy needs to

be reported in an expedited manner via CTEP-AERS as **Grade 3** “*Pregnancy, puerperium and perinatal conditions - Other (pregnancy)*” under the *Pregnancy, puerperium and perinatal conditions* SOC.

Pregnancy needs to be followed **until the outcome is known**. If the baby is born with a birth defect or anomaly, then a second CTEP-AERS report is required.

#### 11.3.6.2 **Pregnancy Loss (Fetal Death)**

Pregnancy loss is defined in CTCAE as “Death in utero.”

Any pregnancy loss should be reported expeditiously, as **Grade 4** “*Pregnancy loss*” under the “*Pregnancy, puerperium and perinatal conditions*” SOC. Do NOT report a pregnancy loss as a Grade 5 event since CTEP-AERS recognizes any Grade 5 event as a patient death

#### 11.3.6.3 **Death Neonatal**

Neonatal death, defined in CTCAE as *Newborn deaths occurring during the first 28 days after birth*” needs to be reported expeditiously, as **Grade 4** “*Death neonatal*” under the “*General disorders and administration*” SOC when the death is the result of a patient pregnancy or pregnancy in partners of men on study. Do NOT report a neonatal death resulting from a patient pregnancy or pregnancy in partners of men on study as a Grade 5 event since CTEP-AERS recognizes any Grade 5 event as a patient death.

### 11.4 **Reporting Requirements for Specialized AEs**

#### 11.4.1 Baseline AEs

Although a pertinent positive finding identified on baseline assessment is not an AE, when possible it is to be documented as “Course Zero” using CTCAE terminology and grade. An expedited AE report is not required if a patient is entered on a protocol with a pre-existing condition (e.g., elevated laboratory value, diarrhea). The baseline AE must be re-assessed throughout the study and reported if it fulfills expedited AE reporting guidelines.

- a. If the pre-existing condition worsens in severity, the investigator must reassess the event to determine if an expedited report is required.
- b. If the AE resolves and then recurs, the investigator must re-assess the event to determine if an expedited report is required.
- c. No modification in grading is to be made to account for abnormalities existing at baseline.

#### 11.4.2 Persistent AEs

A persistent AE is one that extends continuously, without resolution between treatment cycles/courses.

ROUTINE reporting: The AE must be reported only once unless the grade becomes more severe in a subsequent course. If the grade becomes more severe the AE must be reported again with the new grade.

EXPEDITED reporting: The AE must be reported only once unless the grade becomes more severe in the same or a subsequent course.

#### 11.4.3 Recurrent AEs

A recurrent AE is one that occurs and resolves during a cycle/course of therapy and then reoccurs in a later cycle/course.

ROUTINE reporting: An AE that resolves and then recurs during a subsequent cycle/course must be reported by the routine procedures.

EXPEDITED reporting: An AE that resolves and then recurs during a subsequent cycle/course does not require CTEP-AERS reporting unless:

- 1) The grade increases OR
- 2) Hospitalization is associated with the recurring AE.

## 11.5 Exceptions to Expedited Reporting

### 11.5.1 Specific Protocol Exceptions to Expedited Reporting (SPEER)

SPEER: Is a subset of AEs within the Comprehensive Adverse Events and Potential Risks (CAEPR) that contains a list of events that are considered expected for CTEP-AERS reporting purposes. (Formerly referred to as the Agent Specific Adverse Event List (ASAEL).)

AEs listed on the SPEER should be reported expeditiously by investigators to the NCI via CTEP-AERS ONLY if they exceed the grade of the event listed in parentheses after the event. If the CAEPR is part of a combination IND using multiple investigational agents and has an SAE listed on different SPEERs, use the lower of the grades to determine if expedited reporting is required.

### 11.5.2 Special Situations as Exceptions to Expedited Reporting

An expedited report may not be required for a specific protocol where an AE is listed as expected. The exception or acceptable reporting procedures will be specified in the protocol. The protocol specific guidelines supersede the NCI Adverse Event Reporting Guidelines. These special situations are listed under the CTEP-AERS reporting table for this protocol.

## 11.6 Reporting Requirements - Investigator Responsibility

Clinical investigators in the treating institutions and ultimately the Study Chair have the primary responsibility for AE identification, documentation, grading, and assignment of attribution to the investigational agent/intervention. It is the responsibility of the treating physician to supply the medical documentation needed to support the expedited AE reports in a timely manner.

Note: All expedited AEs (reported via CTEP-AERS) must also be reported via routine reporting. Routine reporting is accomplished via the Adverse Event (AE) Case Report Form (CRF) within the study database.

## 11.7 General Instructions for Expedited Reporting via CTEP-AERS

The descriptions and grading scales found in the NCI Common Terminology Criteria for Adverse Events (CTCAE) version 5.0 will be utilized for AE reporting and are located on the CTEP website at:

[http://ctep.cancer.gov/protocolDevelopment/electronic\\_applications/etc.htm](http://ctep.cancer.gov/protocolDevelopment/electronic_applications/etc.htm).

All appropriate treatment areas should have access to a copy of the CTCAE.

An expedited AE report for all studies utilizing agents under an NCI IND/IDE must be submitted electronically to NCI via CTEP-AERS at: <https://eapps-ctep.nci.nih.gov/ctepaers>

In the rare situation where Internet connectivity is disrupted, the 24-hour notification is to be made to the NCI for agents supplied under a CTEP IND by telephone call to [contact]. In addition, once Internet connectivity is restored, a 24-hour notification that was phoned in

must be entered into the electronic CTEP-AERS system by the original submitter of the report at the site.

- Expedited AE reporting timelines are defined as:
  - **24-Hour; 5 Calendar Days** - The AE must initially be reported via CTEP-AERS within 24 hours of learning of the event, followed by a complete expedited report within 5 calendar days of the initial 24-hour report.
  - **7 Calendar Days** - A complete expedited report on the AE must be submitted within 7 calendar days of the investigator learning of the event.
- Any event that results in a persistent or significant incapacity/substantial disruption of the ability to conduct normal life functions, or a congenital anomaly/birth defect, or is an IME, which based upon the medical judgment of the investigator may jeopardize the patient and require intervention to prevent a serious AE, must be reported via CTEP-AERS **if the event occurs following investigational agent administration.**
- Any death occurring within 30 days of the last dose, regardless of attribution to an agent/intervention under an NCI IND/IDE requires expedited reporting **within 24 hours.**
- Any death occurring greater than 30 days of the last dose with an attribution of possible, probable, or definite to an agent/intervention under an NCI IND/IDE requires expedited reporting **within 24 hours.**

CTEP-AERS Medical Reporting includes the following requirements as part of the report: 1) whether the patient has received at least one dose of an investigational agent on this study; 2) the characteristics of the adverse event including the *grade* (severity), the *relationship to the study therapy* (attribution), and the *prior experience* (expectedness) of the adverse event; 3) the phase (1, 2, or 3) of the trial; and 4) whether or not hospitalization or prolongation of hospitalization was associated with the event.

**Any medical documentation supporting an expedited report (e.g., H & P, admission and/or notes, consultations, ECG results, etc.) MUST be faxed within 48-72 hours to the NCI. NOTE: English is required for supporting documentation submitted to the numbers listed below in order for the NCI to meet the regulatory reporting timelines.**

Fax supporting documentation for AEs related to investigational agents supplied under a CTEP IND to: **[contact]** (back-up: [contact]).

Also: Fax or email supporting documentation to COG for all IND studies ([contact]; email: [[contact]](mailto:[contact]); Attention: COG AERS Coordinator).

- **ALWAYS include the ticket number on all faxed documents.**
- **Use the NCI protocol number and the protocol-specific patient ID provided during trial registration on all reports.**

**11.8 Reporting Table for Late Phase 2 and Phase 3 Studies**

Expedited Reporting Requirements for Adverse Events that Occur on Studies under an IND/IDE within 30 Days of the Last Administration of the Investigational Agent/Intervention

FDA REPORTING REQUIREMENTS FOR SERIOUS ADVERSE EVENTS (21 CFR Part 312)  NOTE: Investigators MUST immediately report to the sponsor (NCI) ANY Serious Adverse Events, whether or not they are considered related to the investigational agent(s)/intervention (21 CFR 312.64) An adverse event is considered serious if it results in ANY of the following outcomes:          1) Death.          2) A life-threatening adverse event.          3) Any AE that results in inpatient hospitalization or prolongation of existing hospitalization for ≥ 24 hours. This does not include hospitalizations that are part of routine medical practice.          4) A persistent or significant incapacity or substantial disruption of the ability to conduct normal life functions.          5) A congenital anomaly/birth defect.          6) Important Medical Events (IME) that may not result in death, be life threatening, or require hospitalization may be considered serious when, based upon medical judgment, they may jeopardize the patient or subject and may require medical or surgical intervention to prevent one of the outcomes listed in this definition. (FDA, 21 CFR 312.32; ICH E2A and ICH E6.)
				

ALL SERIOUS adverse events that meet the above criteria MUST be immediately reported to the NCI via CTEP-AERS within the timeframes detailed in the table below.
				
Hospitalization	Grade 1 Timeframes	Grade 2 Timeframes	Grade 3 Timeframes	Grade 4 & 5 Timeframes
Resulting in Hospitalization ≥ 24 hrs	7 Calendar Days			24-Hour Notification 5 Calendar Days
Not resulting in Hospitalization ≥ 24 hrs	Not Required		7 Calendar Days	

NOTE: Protocol specific exceptions to expedited reporting of serious adverse events are found in the Specific Protocol Exceptions to Expedited Reporting (SPEER) portion of the CAEPR. Additional Special Situations as Exceptions to Expedited Reporting are listed below.
 
Expedited AE reporting timelines are defined as:          “24-Hour; 5 Calendar Days” - The AE must initially be reported via CTEP-AERS within 24 hours of learning of the AE, followed by a complete expedited report within 5 calendar days of the initial 24-hour notification.          “7 Calendar Days” - A complete expedited report on the AE must be submitted within 7 calendar days of learning of the AE.
				

SAEs that occur more than 30 days after the last administration of investigational agent/intervention and have an attribution of possible, probable, or definite require reporting as follows:  Expedited 24-hour notification followed by complete report within 5 calendar days for:
 
 
• All Grade 4, and Grade 5 AEs
 
 
Expedited 7 calendar day reports for:
 
 
• Grade 2 adverse events resulting in hospitalization or prolongation of hospitalization
 
• Grade 3 adverse events
 
				

### 11.9 Protocol Specific Additional Instructions and Reporting Exceptions

- **Grades 1- 4 myelosuppression (anemia, neutropenia, thrombocytopenia, leukopenia, lymphopenia) do not require expedited reporting unless it is associated with hospitalization.**

### 11.10 Routine Reporting of Adverse Events

**Note:** The guidelines below are for routine reporting of study specific adverse events on the COG case report forms and do not affect the requirements for CTEP-AERS reporting.

Routine reporting is accomplished via the Adverse Event (AE) Case Report Form (CRF) within the study database. For this study, routine reporting will include all CTEP-AERS reportable events and Grade 3 and higher Adverse Events.

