### 1.2 Secondary Aims

1.2.1 To further define XL184 related toxicities in pediatric, adolescent and young adult patients.

1.2.2 To further define XL184 pharmacokinetics in the pediatric and adolescent patients.

1.2.3 To estimate 1-year time to progression, progression free survival (PFS) and overall survival for each stratum, and if feasible to compare to historical controls.

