#### 5.1.1 Non-Hematological Dose-Limiting Toxicity

- Any Grade 4 non-hematological toxicity
- Any Grade 3 non-hematological toxicity with the specific exception of:
  - Grade 3 nausea and vomiting of less < 3 days duration
  - Grade 3 diarrhea  $\leq$  3 days duration
  - Grade 3 liver enzyme elevation including ALT/AST/GGT/bilirubin that return to levels that meet initial eligibility criteria within 7 days of study drug interruption and that do not recur upon re-challenge with study drug. Note: For the purposes of this trial the ULN for ALT is defined as 45 U/L and the ULN for AST is defined as 50 U/L. See [Section 5.7](#) for dose modifications for liver toxicity. Adverse event grades will be based on increases above the upper limit of normal, regardless of the subject's baseline. See appendix XI for toxicity-specific grading table.
  - Grade 3 fever or infection < 5 days duration.
  - Grade 3 hypophosphatemia, hypokalemia, hypocalcemia and/or hypomagnesemia responsive to supplementation
  - Grade 3 asymptomatic amylase or lipase elevation that resolves to Grade 1 within 7 days of study drug interruption and that does not recur upon re-challenge with XL184. See [Section 5.8](#) for dose modifications for pancreatic toxicity.
  - Grade 3 proteinuria (urine protein/creatinine (P/C) ratio > 1.9) unless it is confirmed with a second measurement within 72 hours
- Any Grade 2 non-hematological toxicity that persists for  $\geq$  7 days and is considered sufficiently medically significant or sufficiently intolerable by patients that it requires treatment interruption
- Dose-limiting hypertension
  - Any Grade 4 hypertension
  - A blood pressure > 25 mmHg above the ULN confirmed by repeated measurement on the same day is dose limiting. For pediatric patients ULN is the 95th percentile for age, height, and gender ([Appendix V](#)) and for patients  $\geq$  18 years of age ULN is 140/90 mmHg.
  - In patients who begin antihypertensive therapy a blood pressure > 10 mmHg but  $\leq$  25 mmHg above the ULN ([Appendix V](#)) for > 14 days is dose limiting.
- QTc prolongation > 500 ms that persists despite correction of serum electrolyte abnormalities will be considered dose limiting

- Grade 2 or higher allergic reactions that necessitate discontinuation of study drug will not be considered a dose-limiting toxicity.

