#### 5.5 Dose Modifications for Hypertension

- **Baseline blood pressure (BP)** is defined as the blood pressure obtained at the examination used for study enrollment. This baseline BP should be obtained as follows: 1) Obtain 3 serial blood pressures from the same extremity with the patient in the same position at rest with an appropriately sized cuff that are separated by at least 5 minutes. Avoid using the lower extremity if possible. 2) Average the systolic blood pressure from the 2nd and 3rd measurements. 3) Average the diastolic blood pressure from the 2nd and 3rd measurements. 4) The baseline BP is the average of the systolic over the average of the diastolic measurements.
- **Elevation** in either the systolic or diastolic blood pressure should be considered when following the algorithm below.
- **The (ULN)** is defined as a BP equal to the 95th percentile for age, height, and gender for pediatric patients (See [Appendix V](#)) For adult patients (ages  $\geq 18$  years), the ULN is 140/90 mmHg.
- The NCI CTCAE will be utilized to determine the grade of hypertension for reporting purposes.
- Elevated BP measurements should be repeated on the same day to confirm the elevation. If confirmed, patients with elevated BP should have BP measurements performed at least twice weekly until BP is  $\leq$  ULN.
- The algorithm below will be used to manage XL184- related hypertension.

- Hypertension should be managed with appropriate anti-hypertensive agent(s) as clinically indicated. It is strongly recommended that nephrology or cardiology be consulted in the evaluation and management of hypertension.

Elevations in BP are based on systolic or diastolic pressures.

 Elevated blood pressure (BP) measurements should be repeated on the same day to confirm the elevation. Patients with elevated BP at any time should have BP measurements performed at least twice weekly until BP within the ULN (Upper Limit of Normal).

 ULN for pediatric patients is a BP equal to the 95th percentile for a age, height, and gender-appropriate normal values (see [Appendix V](#)). For adult patients (ages ≥ 18 years) the ULN is 140/90 mmHg.

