## 5.10 Monitoring for Specific Toxicities

### 5.10.1 Growth Plate Toxicity

Patients  $\leq$  18 years of age at enrollment will have a plain AP radiograph of a single proximal tibial growth plate obtained prior to the first dose of protocol therapy.

- a. If patients are found to have a closed tibial growth plate, no further radiographs will be required.
- b. If patients are found to have an open tibial growth plate, then repeat plain AP radiographs of the same tibial growth plate will be obtained prior to Cycles 2, 5 and every 6 cycles thereafter until off protocol therapy.
  - Patients with evidence of growth plate thickening or other changes should have a knee MRI performed to further assess the degree of physal pathology and undergo more frequent x-ray follow up. MRI should be performed without contrast.
  - Patients with knee MRI changes should be managed in an individualized manner. Decisions regarding continuation of XL184 should be made after discussion with the Study Chair or Study Vice-Chair, taking into account the presence of any symptoms referable to the knee as well as the patient's response to XL184. Consultation with an orthopedic surgeon may also be indicated. Plans for follow-up imaging will also be made on an individualized basis, taking into account the presence of symptoms at the knee or other joints as well as the decision to continue XL184 or not.

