### 5.10.2 Thyroid Toxicity

Patients found to have an abnormal TSH level should have a free T4 level measured. Thyroid toxicity will be handled like any other non-hematological toxicity. Guidance on the management of patients who develop hypothyroidism is included below.

Patients with Grade 2 hypothyroidism adequately managed with thyroid hormone replacement may continue on protocol therapy. Patients with Grade 3 or greater hypothyroidism will be considered to have had a dose-limiting toxicity. These patients should be managed according to [Section 5.3](#) and should also be evaluated by an endocrinologist for further management. Patients who enter the study on thyroid replacement should have their medication adjusted to maintain TSH in the normal range.

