### 9.3 Methods of Analysis

Toxicity tables will be constructed to summarize the observed incidence by type of toxicity and grade. A patient will be counted only once for a given toxicity for the worst grade of that toxicity reported for that patient. Toxicity information recorded will include the type, severity, time of onset, time of resolution, and the probable association with the study regimen.

Time-to-event analyses (time to progression, progression-free survival, and overall survival) will be computed when all patients in a stratum have at least one year of follow-up.

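### Routine adverse event reporting starts at Grade 3, so a non-serious outpatient Grade 2 dose-limiting toxicity has no stated route into the toxicity tables

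*Combined protocol and SAP*

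**What the plan says.** Section 11.10 names the adverse event case report form as the channel for routine reporting and sets its content: "routine reporting will include all CTEP-AERS reportable events and Grade 3 and higher Adverse Events".

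Section 5.1.1 lists, among the non-hematological DLTs, a Grade 2 toxicity that lasts at least 7 days and is "considered sufficiently medically significant or sufficiently intolerable by patients that it requires treatment interruption". Under Section 5.3 a DLT means a hold and then resumption at the next lower level. The patient leaves therapy if the toxicity does not resolve within 21 days (weight loss has its own rule) or if a DLT occurs after two reductions (one reduction in the smallest body-surface-area band).

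The analysis has no lower grade limit. Section 9.3 states: "Toxicity tables will be constructed to summarize the observed incidence by type of toxicity and grade". The aim it serves, 1.2.1, reads: "To further define XL184 related toxicities in pediatric, adolescent and young adult patients".

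Section 9.3.4 monitors 18 named toxicities per cycle with a Bayesian rule. It gives no grade and no attribution for the events counted, and it does not mention DLTs.

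**The concern.** The protocol treats certain Grade 2 events as serious enough to interrupt treatment, lower the dose and possibly end therapy. The routine reporting rule does not ask for the same events to be recorded. If sites follow Section 11.10 as written, the final tables could show interruptions and reductions with no adverse event entry to explain them. The tables laid out by type and grade would in practice begin at Grade 3, apart from expedited events.

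This matters for an oral agent given continuously. Fatigue, palmar-plantar erythrodysesthesia and mucositis at Grade 2 are the kind of event that could meet the 7-day interruption criterion, and all three were cycle 1 DLT types in the pediatric phase 1 trial (Section 2.4.1). Section 2.4.1 also says that DLTs in later cycles requiring reduction informed the phase 2 dose.

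A second question is whether the monitoring rule in Section 9.3.4 is fed by data that match what it is meant to count.

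**Working it through.** **1. Tracing a Grade 2 DLT that is not serious and involves no hospitalization**

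- Section 5.1.1: it is a DLT.
- Section 5.3: it triggers a hold and a reduction, with possible removal.
- Section 11.8 table: Grade 2 without hospitalization of 24 hours or more needs no expedited report, so the event is not CTEP-AERS reportable.
- Section 11.10: the event is neither CTEP-AERS reportable nor Grade 3 or higher, so the stated rule does not call for it.
- Section 9.3 and Aim 1.2.1: there is no entry to tabulate.

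**2. How far the expedited route helps**

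Section 11.8 makes a Grade 1–2 event with hospitalization of 24 hours or more reportable, and Section 11.2 adds other serious criteria. Those events then enter routine reporting. The list of exceptions in Section 6.1 narrows this, because a listed event is expedited only if it exceeds the stated grade. By count, 13 of the 18 toxicities in Section 9.3.4 are on that list: 12 at Grade 3 or 4, and hypothyroidism at Grade 2. The expedited route is therefore real but partial.

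**3. DLTs defined without a CTCAE grade**

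Section 5.1.1 defines dose-limiting hypertension partly in mmHg, while Section 5.5 says "The NCI CTCAE will be utilized to determine the grade of hypertension for reporting purposes". Section 5.1.2 includes a cycle delay of more than 21 days from myelosuppression. The documents do not map these to a grade, so a reporting rule based on grade alone does not guarantee that they are recorded as DLTs.

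**4. The monitoring rule: reproducing the plan's figures**

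Inputs from Section 9.3.4 are a Beta(0.52, 2.08) prior, a 20% per-cycle threshold, and a signal at posterior probability of at least 0.70 with at least 2 events. For x events in n cycles:

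P(p > 0.20 | x, n) = upper tail at 0.20 of Beta(0.52 + x, 2.08 + n − x).

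All 13 printed pairs reproduce. In each, the printed n is the largest that reaches 0.70. For example, 2/6 gives 0.7001 and 2/7 gives 0.632; 14/60 gives 0.7135 and 14/61 gives 0.691. The arithmetic of the rule is sound. The open question is which events make up x.

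**5. What the reporting threshold could do to the rule**

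*If the rule means Grade 3 and higher:* the threshold in Section 11.10 matches it and nothing is lost on account of grade.

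*If the rule also means Grade 2 DLTs or other lower-grade events:* x is truncated. At a printed boundary, one missing event removes the signal:

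| Events/cycles | Posterior | One event fewer |
|---|---|---|
| 3/10 | 0.715 | 0.443 |
| 4/14 | 0.730 | 0.501 |
| 6/23 | 0.722 | 0.541 |

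This holds by construction, because these are the rule's own boundaries. It does not say how often an event is missed.

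The next table is an illustration, not an estimate. It assumes independent cycles, 60 cycles in all, and a share f of qualifying cycles reaching the form. The true rates and the values of f are assumptions; the documents give neither. Entries are the probability that the rule signals.

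| f | True rate 30%, checked every cycle | True rate 30%, one look at 60 | True rate 40%, checked every cycle |
|---|---|---|---|
| 1 | 0.966 | 0.900 | 0.999 |
| 0.75 | 0.770 | 0.489 | 0.966 |
| 0.5 | 0.373 | 0.058 | 0.648 |
| 0.25 | 0.086 | under 0.001 | 0.157 |

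The effect runs from none (f = 1, or a rule limited to Grade 3 and higher) to large. The documents do not say which applies.

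**The case against.** The strongest reply is that collecting Grade 3 and higher is a disclosed, deliberate choice that limits data burden, and that Section 11.10 says what reporting will include, not what it is limited to. The case report forms are held outside the documents (Section 12.0) and may have DLT or dose-modification fields. Other records also exist. The Study Chair must be told of any dosage modification (Section 5.2), the diary of tablets prescribed and taken is uploaded each cycle (Appendix III), and the therapy delivery maps ask for held doses. All of this stands, and it is why the conclusion is conditional on the forms. But a notification, a tablet count or a comment about a held dose is not a graded adverse event, and no section says it feeds the Section 9.3 tables.

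A reader might infer four stronger conclusions. The documents do not support them.

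- *The Bayesian rule is undercounted now.* Section 9.3.4 states no grade and does not use DLTs. Its list largely follows the phase 1 DLTs and most frequent events, and a Grade 3 and higher reading is plausible.
- *No low-grade event reaches the data.* Hospitalized or otherwise serious ones do, subject to the exceptions list.
- *The trial will report almost no hypothyroidism.* Section 5.10.2 says "Patients with Grade 2 hypothyroidism adequately managed with thyroid hormone replacement may continue on protocol therapy", so treated Grade 2 cases may well go unrecorded on the adverse event form. But Section 2.4.1 gives no grade split for hypothyroidism, so the loss cannot be sized.
- *The trial fails to confirm the tolerability of its dose.* That is not a stated aim; Aim 1.2.1 is to define toxicity further.

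**Conclusion.** The mismatch between Sections 5.1.1 and 11.10 is real. Under the stated rules, a Grade 2 DLT that is not serious and involves no hospitalization does not reach the adverse event form. The Section 9.3 tables and Aim 1.2.1 would therefore omit one class of the protocol's own DLTs. This assumes that the adverse event form is the source for those tables and that no form outside the documents records the events. No Grade 2 DLT rate is given, so the number lost cannot be stated.

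For Section 9.3.4 the supportable finding is narrower: the rule has no event definition to set beside the reporting threshold. Whether it is undercounted depends on that missing definition. The primary response and disease-control analyses are not affected. This is a cheap improvement to the plan, not a flaw in its design.

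**What to change.** - **Section 11.10:** add to routine reporting every event that meets a DLT definition in Section 5.1.1 or 5.1.2, whatever its grade, and any Grade 2 event that leads to a hold, a dose reduction or removal from therapy. If a DLT or dose-modification form already records these with type and grade, citing that form is enough.
- **Section 9.3:** tabulate DLTs by type, grade and cycle.
- **Section 9.3.4:** state that the rule counts Grade 3 and higher events plus DLTs of the listed types, and state the attribution required. Say also whether a toxicity that continues into a later cycle counts again, since Section 11.4.2 has a persistent event reported once while the rule counts cycles.
- **Optional:** record the thyroid and growth-plate findings at any grade. The TSH tests and radiographs are already required, but the added entry is a judgement about data burden.

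The cost is wording plus modest extra data entry at sites. No new test and no change in treatment is needed. The reported toxicity burden may look somewhat less favourable.
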